7.6 Dose Adjustments and Adverse Reaction Management

Dose adjustments for toxicity of duvelisib and nivolumab are detailed below and are excerpted from the duvelisib package insert and the nivolumab package insert^{11,22}. Where appropriate, management guidelines for immune-related adverse events in patients receiving immune checkpoint therapy, from the American Society of Clinical Oncology (ASCO) Practice Guidelines has been included²³. The table below is not comprehensive and clinicians should refer to the ASCO Practice Guidelines for more detailed management recommendations. When possible, biopsies should be pursued to help determine the study drug(s) responsible for a given toxicity.

Table 7.6 Dose Adjustments for Toxicity

Toxicity	Adverse Reaction Grade	Recommended Management
Nonhematologic Adverse Reactions		
Infections	Grade 3 or higher infection	
Duvelisib
 
 - Withhold duvelisib until resolved - Resume at the same or reduced dose 
Nivolumab
 
 - Withhold nivolumab until resolved - Resume at same dose
	Clinical CMV infection or viremia (positive PCR or antigen test)	
Duvelisib
 
 - Withhold duvelisib until resolved - Resume at the same or reduced dose - If duvelisib is resumed, monitor patients for CMV reactivation by PCR or antigen test at least monthly

Toxicity	Adverse Reaction Grade	Recommended Management
		
Nivolumab
 
 - Withhold nivolumab until resolved - Resume at same dose
	PJP	
Duvelisib
 
 - For suspected PJP, withhold duvelisib until evaluated - For confirmed PJP, discontinue duvelisib 
Nivolumab
 
 - Withhold nivolumab until resolved
Non-infectious diarrhea or colitis	Mild/moderate diarrhea (Grade 1-2, up to 4 stools per day over baseline) and responsive to antidiarrheal agents, OR Asymptomatic (Grade 1) colitis	
Duvelisib
 
 - No change in dose - Initiate supportive therapy with antidiarrheal agents as appropriate - Monitor at least weekly until resolved 
Nivolumab
 
 - Continue nivolumab or hold until symptoms resolve
	Mild/moderate diarrhea (Grade 1-2, up to 6 stools per day over baseline) and unresponsive to antidiarrheal agents	
Duvelisib
 
 - Withhold duvelisib until resolved - Initiate supportive therapy with systemic steroids - Monitor at least weekly until resolved - Resume at a reduced dose - Gastroenterology consultation, recommend endoscopy and biopsy 
Nivolumab
 
 - Withhold nivolumab until resolved - Resume at same dose - Support with systemic steroids, gastroenterology consultation, recommend endoscopy and biopsy
	Abdominal pain, stool with mucus or blood, change in bowel habits, peritoneal signs, OR Severe diarrhea (Grade 3, >6 stools per day over baseline)	
Duvelisib
 
 - Withhold duvelisib until resolved - Initiate supportive therapy with enteric acting steroids (e.g., budesonide) or systemic steroids - Monitor at least weekly until resolved - Resume at a reduced dose

Toxicity	Adverse Reaction Grade	Recommended Management
		
 - For recurrent Grade 3 diarrhea or recurrent colitis of any grade, discontinue duvelisib 
Nivolumab
 
 - Withhold nivolumab until resolved - Resume at same dose - Systemic steroids, gastroenterology consultation and biopsy - If no improvement in 3-5 days, consider addition of infliximab
	Life-threatening, grade 4	
Duvelisib
 
 - Discontinue duvelisib 
Nivolumab
 
 - Permanently discontinue nivolumab - Systemic steroids, gastroenterology consultation and biopsy - If no improvement in 3-5 days, consider addition of infliximab
Cutaneous reactions	Grade 1	
Duvelisib
 
 - No change in dose - Initiate supportive care with emollients, antihistamines (for pruritus), or topical steroids - Monitor closely 
Nivolumab
 
 - Continue nivolumab - Support with topical emollients and/or mild-moderate potency topical corticosteroids
	Grade 2	
Duvelisib
 
 - Consider holding duvelisib, restart at same dose - Initiate supportive care with emollients, antihistamines (for pruritus), or topical steroids - Monitor closely 
Nivolumab
 
 - Consider holding nivolumab until resolved - Resume at same dose once improved to grade 1

Toxicity	Adverse Reaction Grade	Recommended Management
		
 - Support with topical emollients and/or mild-moderate potency topical corticosteroids - Consider systemic steroids at 1mg/kg and taper over 4 weeks - Consider skin biopsy
	Grade 3	
Duvelisib
 
 - Withhold duvelisib until resolved - Initiate supportive care with emollients, antihistamines (for pruritus), or topical steroids - Monitor at least weekly until resolved - Resume at reduced dose - If severe cutaneous reaction does not improve, worsens, or recurs, discontinue duvelisib 
Nivolumab
 
 - Hold nivolumab until resolved - Resume at same dose once improved to grade 1 - Support with topical emollients and high-potency steroids, dermatology consultation - Systemic steroids at 1-2mg/kg and taper over 4 weeks - Consider dermatology consultation - Skin biopsy recommended
	Grade 4	
Duvelisib
 
 - Discontinue duvelisib 
Nivolumab
 
 - Hold nivolumab - Dermatology consultation to determine if appropriate to resume upon resolution - Systemic steroids administered IV -Skin biopsy recommended
	SJS, TEN, DRESS (any grade) or life-threatening skin toxicity	
Duvelisib
 
 - Discontinue duvelisib 
Nivolumab
 
 - Discontinue nivolumab

Toxicity	Adverse Reaction Grade	Recommended Management
Pneumonitis without suspected infectious cause	Grade 1 – asymptomatic. If repeat imaging with progression	
Duvelisib
 
 - Withhold duvelisib - If pneumonitis recovers to Grade 0 or 1, duvelisib may be resumed at same dose - If no improvement should treat as grade 2 
Nivolumab
 
 - Withhold nivolumab until resolved - Resume at same dose - If no improvement, treat as grade 2
	Moderate (Grade 2) symptomatic pneumonitis	
Duvelisib
 
 - Withhold duvelisib - Treat with systemic steroid therapy - If pneumonitis recovers to Grade 0 or 1, duvelisib may be resumed at reduced dose - If non-infectious pneumonitis recurs or patient does not respond to steroid therapy, discontinue duvelisib 
Nivolumab
 
 - Withhold nivolumab until resolved to grade 0-1 - Resume at same dose - Prednisone 1-2mg/kg/d, with long taper - Consider pulmonology consultation, bronchoscopy and biopsy, empiric antibiotics - Monitor closely, if no improvement in 2-3 days treat as grade 3
	Severe (Grade 3) or Grade 4 life-threatening pneumonitis	
Duvelisib
 
 - Discontinue duvelisib - Treat with systemic steroid therapy 
Nivolumab
 
 - Permanently discontinue nivolumab - Treat with high dose IV steroids, consider infliximab, empiric antibiotics - Pulmonary and infectious disease consultations and biopsy if able
ALT/AST elevation	3 to 5 x upper limit of normal (ULN) (Grade 2)	
Duvelisib
 
 - Maintain duvelisib dose - Monitor at least weekly until return to < 3 x ULN

Toxicity	Adverse Reaction Grade	Recommended Management
		
Nivolumab
 
 - Withhold nivolumab until resolved to grade 1 - Resume at same dose - Consider steroids if abnormality persists and clinical symptoms
	> 5 to 20 × ULN (Grade 3)	
Duvelisib
 
 - Withhold duvelisib and monitor at least weekly until return < 3 × ULN - Resume duvelisib at same dose (first occurrence) or at a reduced dose for subsequent occurrence 
Nivolumab
 
 - Permanently discontinue nivolumab - Start steroids with methylprednisolone at 1-2mg/kg/d - Consider liver biopsy
	> 20 × ULN (Grade 4)	
Duvelisib
 
 - Discontinue duvelisib - Systemic steroid treatment 
Nivolumab
 
 - Permanently discontinue nivolumab - Start steroids with methylprednisolone at 1-2mg/kg/d - Avoid infliximab - Hepatology consultation, consider liver biopsy
Hematologic Adverse Reactions		
Neutropenia	Absolute neutrophil count (ANC) 500 to 1000 cells/µL	
Duvelisib
 
 - Maintain duvelisib dose - Monitor ANC at least weekly 
Nivolumab
 
 - Withhold nivolumab until resolved if it is felt to contribute to the neutropenia, and otherwise continue nivolumab as previously - Resume at same dose
	ANC less than 500 cells/µL	
Duvelisib
 
 - Withhold duvelisib

Toxicity	Adverse Reaction Grade	Recommended Management
		
 - Monitor ANC until > 500 cell/uL - Resume duvelisib at same dose (first occurrence) or at a reduced dose for subsequent occurrence 
Nivolumab
 
 - Withhold nivolumab until resolved if it is felt to contribute to the neutropenia, and otherwise continue nivolumab as previously - Resume at same dose 
*If concern for auto-immune neutropenia, then hold nivolumab and follow practice guidelines

Thrombocytopenia	Platelet count 25K to < 50K cells/ μ L (Grade 3) with Grade 1 bleeding	
Duvelisib
 
 - No change in dose - Monitor platelet counts at least weekly 
Nivolumab
 
 - Withhold nivolumab until resolved - Resume at same dose
	Platelet count 25K to < 50K cells/ μ L with grade 2 bleeding OR platelet count <25K cells/ μ L (Grade 4)	
Duvelisib
 
 - Withhold duvelisib - Monitor platelet count until > 25K cells/uL and resolution of bleeding if applicable. - Resume duvelisib at same dose (first occurrence) or resume at a reduced dose for subsequent occurrence 
Nivolumab
 
 - Withhold nivolumab until resolved - Resume at same dose 
*If concerned for autoimmune thrombocytopenia, hold nivolumab and follow practice guidelines

Table 7.7 Dose Reductions for Duvelisib

Initial Dose	Decreased Dose
15mg Daily	None

25mg Daily	15mg Daily
25mg BID	25mg Daily

Note: If patient is on dose level 1, 15mg daily and has a dose interruption, duvelisib will be resumed at same dose. If patient subsequently requires another dose interruption at this level for the same toxicity, duvelisib should be discontinued. No more than 2 dose reductions for the same side effect are allowed for any patient, irrespective of starting dose.

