11.2 Diarrhea/Colitis

Diarrhea and colitis were also seen frequently. Median time to onset was 4 months, with the majority of cases occurring before 8 months, and symptoms could be prolonged (median duration 0.5 months). For grade 1-2 diarrhea or asymptomatic colitis, initiate supportive care with antidiarrheal agents, continue medication and monitor weekly until resolution. If unresponsive to antidiarrheals then duvelisib should be held and enteric steroids such as budesonide should be started. Duvelisib may then be restarted at a reduced dose as deemed clinically appropriate by the treating physician.

For subjects with abdominal pain, stools with mucus or blood, or severe diarrhea, hold duvelisib and start systemic or enteric steroids. If possible, a colonoscopy and work-up for immune-mediated colitis should be performed. Restart duvelisib at a reduced dose upon resolution of symptoms to less than or equal to CTCAE Grade 1. For recurrent events, duvelisib should be permanently discontinued.

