11.3 Cutaneous Reactions

Cutaneous reactions including drug reaction with eosinophilia and systemic symptoms (DRESS) and toxic epidermal necrolysis (TEN) occurred with duvelisib. Median time to onset was 3 months with a median event duration of 1 month. Patients often presented with pruritic, erythematous or maculo-papular rash. Subjects should report rashes, sores, ulcers on skin, lips, mouth, blisters, rash, fevers promptly. Subjects with Grade 1-2 reactions should continue duvelisib at the current dose, supported with

emollients, anti-histamines, topical steroids and close monitoring. If reaction is more severe, duvelisib should be held, and steroids (topical and systemic) and antihistamines should be given. Patients should be monitored at least weekly. Duvelisib should be discontinued if cutaneous reactions recur. If subjects experience, SJS, TEN, or DRESS of any grade, discontinue duvelisib.

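### Table 7.6 has two nivolumab instructions that can apply to the same grade 4 skin reaction, and sections 11.2 and 11.3 differ from the table with no text saying which governs

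*Combined protocol and SAP*

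**What the plan says.** Section 7.6 introduces Table 7.6 as guidance excerpted from the two package inserts, supplemented by a practice guideline, and says that it is not comprehensive. Its action column is headed as recommended management.

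- **Skin, grade 4 (Table 7.6).** Duvelisib is discontinued. Nivolumab is held, with this instruction on its return: "Dermatology consultation to determine if appropriate to resume upon resolution".
- **Skin, next row (Table 7.6).** The row covers "SJS, TEN, DRESS (any grade) or life-threatening skin toxicity". Duvelisib is discontinued, and for nivolumab the entry is "Discontinue nivolumab".
- **Grade 1-2 diarrhea unresponsive to antidiarrheals.** Table 7.6: "Initiate supportive therapy with systemic steroids". Section 11.2: "enteric steroids such as budesonide should be started".
- **Skin, grade 2.** Table 7.6: "Consider holding duvelisib, restart at same dose". Section 11.3: "Subjects with Grade 1-2 reactions should continue duvelisib at the current dose". For anything more severe, section 11.3 holds duvelisib; it names discontinuation only for recurrence and for SJS, TEN or DRESS.
- **Pneumonitis, grade 1 with progression on repeat imaging (Table 7.6).** Duvelisib is withheld, then: "If pneumonitis recovers to Grade 0 or 1, duvelisib may be resumed at same dose". The following line sends a patient without improvement to the grade 2 row.

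Section 11.0 describes its content as suggestions that depend on clinical context, and refers the reader to section 7.6 for adverse events with either drug.

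**The concern.** A dose-modification table should lead two physicians with the same patient and the same grade to the same action. Here a patient with a grade 4 skin reaction that is also life-threatening fits two adjacent rows. One row leaves a route back to nivolumab and the other closes it. Whether that patient is re-exposed then depends on which row is read.

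The differences between Table 7.6 and section 11 raise the same problem at a lower level. A physician who follows one text can depart from the other on the steroid given, on whether duvelisib is held or stopped for good, and on whether a recurrence ends treatment. Section 11 presents diarrhea, colitis and skin reactions as known effects of duvelisib, so these lines are likely to be used.

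**Working it through.** No figure in the plan is involved and no arithmetic applies. The check is a comparison of the texts, row by row.

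**Step 1. Can one skin event meet both Table 7.6 rows?**

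| Row | Duvelisib | Nivolumab |
|---|---|---|
| Grade 4 | Discontinue | Hold; dermatology advises on resuming |
| SJS/TEN/DRESS, or life-threatening | Discontinue | Discontinue |

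The first row is defined by grade. The second is defined by named syndromes or by threat to life. The definitions are not mutually exclusive, and no note says that one row excludes the other. The table itself attaches the life-threatening label to grade 4 in its diarrhea row and again in its pneumonitis row. It does not do so in its liver-enzyme or platelet rows. Carried over to skin, the label puts a grade 4 reaction in both rows. Even without that carry-over, any grade 4 reaction that is in fact life-threatening meets both. The duvelisib columns agree, so the conflict is on nivolumab alone.

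**Step 2. Where do Table 7.6 and section 11 differ?**

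| Event | Table 7.6 | Section 11 |
|---|---|---|
| Grade 1-2 diarrhea unresponsive to antidiarrheals | Systemic steroids | Enteric steroids (11.2) |
| Grade 4 skin reaction other than SJS/TEN/DRESS | Discontinue duvelisib | Hold duvelisib, as for anything above grade 2 (11.3) |
| Recurrent diarrhea or colitis | Stop duvelisib for recurrent grade 3 diarrhea or recurrent colitis of any grade | Stop duvelisib for recurrent events, no grade given (11.2) |
| Recurrent skin reaction | Stop duvelisib if a severe reaction recurs, worsens or does not improve | Stop duvelisib if cutaneous reactions recur, no severity given (11.3) |

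In the first line both texts hold duvelisib and allow a restart at a reduced dose, so only the steroid differs. In the second, a hold leaves resumption possible where the table does not. In the last two, section 11 is broader as worded. Both sentences follow text about more severe events; if they were meant to cover only those events, the gap narrows, but they do not say so.

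**Step 3. Does any text settle precedence?** Section 11.0 points to section 7.6, and section 7.6 points to an outside practice guideline. Neither says which prevails where they differ.

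**Step 4. Two items that are unclear but not contradictory.**

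- *Grade 1 pneumonitis.* The hold needs grade 1 plus progression on imaging. Resumption needs recovery to grade 0 or 1, and no improvement moves the patient to the grade 2 row. The row therefore expects improvement first. However, its only stated threshold includes the grade that triggered the hold, and improvement within grade 1 is not defined. Nivolumab in the same row waits until resolution.
- *Grade 2 skin.* The table asks the physician to consider a hold, and section 11.3 says to continue. A physician who considers a hold and decides against it complies with both.

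**The case against.** The best defense is that both texts are advisory. Section 11.0 offers suggestions and sends the reader to section 7.6, and Table 7.6 gives recommendations and says that it is incomplete. The two skin rows are listed separately, which suggests that the authors meant a distinction. Section 8.2.1 defines life-threatening by risk of death at the time of the event, without reference to grade. The grade 4 row also does not direct re-exposure: a physician who never resumes nivolumab satisfies both rows.

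Much of this stands as context. It means that the overlap for *every* grade 4 skin reaction is an inference from other rows and is not stated in the skin rows. It does not remove the problem. If a distinction was meant, the table does not give it, and the row that allows resumption has no limit that excludes a life-threatening case. The advisory status of section 11 cannot help here, because both skin rows lie inside Table 7.6. For the differences between section 11 and the table, a cross-reference is weaker than a precedence rule.

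A reader might infer more than the documents support:

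- *That the grade 1 pneumonitis hold is empty, because its release condition is met on the first day.* The row requires recovery and deals separately with no improvement, so it is loosely worded but not void.
- *That the grade 2 skin instructions are opposites.* One is permissive, so they differ in emphasis.
- *That practice will diverge between sites.* Section 5.1 names one study site; any variation is between treating physicians.
- *That the trial's analyses would be distorted.* Sections 14.2.3.1 to 14.2.3.5 plan no analysis of dose intensity or of discontinuation counts. Safety is tabulated by maximum grade, so a grade 4 skin reaction is recorded as grade 4 whichever row is then followed. Only acute dose-limiting toxicities drive escalation. Late toxicities do inform the recommended phase II dose, but the documents do not show that these wording differences would change it.

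**Conclusion.** The point holds in a limited form. Its core is one conflict inside Table 7.6, on nivolumab, for a skin reaction that is both grade 4 and life-threatening. It rests on the rows not being mutually exclusive and is supported by the table's own pairing of the two terms in two other toxicities. Beyond that there are four differences between Table 7.6 and sections 11.2 and 11.3: one on the steroid, one on hold versus discontinuation of duvelisib at grade 4 skin, and two on recurrence. The recurrence pair assumes that the section 11 sentences are read as worded. The grade 1 pneumonitis and grade 2 skin lines need clarification only.

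Nothing here alters the sample size, the monitoring boundaries or the stated operating characteristics. The reason to act is patient safety, chiefly whether nivolumab can be given again after a life-threatening skin reaction.

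**What to change.** Reconcile the passages by amendment:

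1. In Table 7.6, make the grade 4 and life-threatening skin rows mutually exclusive, or give them a single nivolumab instruction.
2. Bring section 11.2 and Table 7.6 into agreement on the steroid for grade 1-2 diarrhea unresponsive to antidiarrheals and on the recurrence rule.
3. Bring section 11.3 and Table 7.6 into agreement on duvelisib above grade 2, on the recurrence rule, and on the emphasis at grade 2.
4. State in sections 7.6 and 11.0 which text governs where they differ.
5. In the grade 1 pneumonitis row, state what counts as improvement before duvelisib is resumed.

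Which clinical rule applies in each case is for the investigators to decide; this review takes no view. The cost is wording in Table 7.6 and sections 7.6, 11.0, 11.2 and 11.3, with no added procedures, visits or patients.

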8.2 Serious Adverse Events

8.2.1 SAE Definitions

A Serious Adverse Event (SAE) is any untoward medical occurrence that at any dose:

- Results in death
- Is life threatening (defined as an event in which the subject was at risk of death at the time of the event; it does not refer to an event which hypothetically might have caused death if it were more severe)
- Requires inpatient hospitalization or causes prolongation of existing hospitalization
- Results in persistent or significant disability/incapacity
- Results in a congenital anomaly/birth defect
- Is an important medical event (defined as a medical event(s) that may not be immediately life-threatening or result in death or hospitalization but, based upon appropriate medical and scientific judgment, may jeopardize the subject or may require intervention [e.g., medical, surgical] to prevent one of the other serious outcomes listed in the definition above. (Examples of such events include, but are not limited to, intensive treatment in an emergency room or at home for allergic bronchospasm; blood dyscrasias or convulsions that do not result in hospitalization.) Potential drug induced liver injury (DILI) is also considered an important medical event.

Suspected transmission of an infectious agent (e.g., pathogenic or nonpathogenic) via the study drug is an SAE (e.g. contamination of drug product). Although pregnancy, overdose, new cancers, and potential drug induced liver injury (DILI) are not always serious by regulatory definition, these events must be handled as SAEs. Any component of a study endpoint that is considered related to study therapy (e.g., death is an endpoint, if death occurred due to anaphylaxis, anaphylaxis must be reported) should be reported as an SAE (see below for reporting details).

The following hospitalizations will not be considered SAEs in this study:

- A visit to the emergency room or other hospital department < 24 hours, that does not result in admission, unless otherwise deemed an important medical or life-threatening event
- Elective surgery, planned prior to signing study consent
- Admissions as per protocol for a planned medical/surgical procedure

- Routine health assessment requiring admission for baseline/trending of health status (e.g. routine colonoscopy)
- Medical/surgical admission not intended to remedy ill health and/or planned prior to entry into the study. Appropriate documentation is required in these cases

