8.8 Potential Drug Induced Liver Injury

Whenever possible, timely confirmation of initial liver-related laboratory abnormalities should occur prior to the reporting of a potential drug-induced liver injury (DILI) event. All occurrences of potential DILIs, meeting the defined criteria below, must be reported as SAEs (see Section 8.1.1 for reporting details).

Potential drug induced liver injury is defined as:

- AT (ALT or AST) elevation > 3 times upper limit of normal (ULN) AND
- Total bilirubin > 2 times ULN, without initial findings of cholestasis (elevated serum alkaline phosphatase), AND
- No other immediately apparent possible causes of AT elevation and hyperbilirubinemia, including, but not limited to, viral hepatitis, pre-existing chronic or acute liver disease, or the administration of other drug(s) known to be hepatotoxic.

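### No ALT/AST row in Table 7.6 has a bilirubin condition, so a patient who meets the section 8.8 potential-DILI definition can stay on duvelisib at 3-5 x ULN, or resume it at full dose after >5 to 20 x ULN

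*Combined protocol and SAP*

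**What the plan says.** Table 7.6 (section 7.6) manages liver enzymes in three rows defined by ALT/AST alone.

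- **3 to 5 x ULN (Grade 2).** Duvelisib: "Maintain duvelisib dose - Monitor at least weekly until return to < 3 x ULN". Nivolumab: "Withhold nivolumab until resolved to grade 1", then resumed at the same dose.
- **>5 to 20 x ULN (Grade 3).** Duvelisib: "Withhold duvelisib and monitor at least weekly until return" below 3 x ULN, then the same dose after a first occurrence and a reduced dose after a later one. Nivolumab: "Permanently discontinue nivolumab - Start steroids with methylprednisolone".
- **>20 x ULN (Grade 4).** Both drugs are stopped for good.

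The table has no bilirubin row and no drug-induced liver injury (DILI) row.

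Section 8.8 defines potential DILI by three joint criteria: "AT (ALT or AST) elevation > 3 times upper limit of normal (ULN) AND" "Total bilirubin > 2 times ULN, without initial findings of cholestasis", and "No other immediately apparent possible causes of AT elevation and hyperbilirubinemia". Such cases must be reported as SAEs. Section 8.2.1 adds that "Potential drug induced liver injury (DILI) is also considered an important medical event". Neither section says what to do with either drug.

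**The concern.** The dosing table and the liver-injury definition overlap but are not connected. Section 8.8 singles out a combination of findings as serious enough to report every time. The dosing table looks at only one part of that combination. In the lowest band it gives a positive instruction to keep dosing, and in the middle band it permits full-dose rechallenge on an ALT/AST threshold alone. A persisting or rising bilirubin triggers no duvelisib action in either band.

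At stake is continued or repeated exposure to a suspected hepatotoxin in a patient whom the protocol itself classes as a potential DILI case. The entry rules make it likely that such an injury is new on study. Section 4.1 requires normal ALT/AST (or up to 2.5 x ULN with liver metastasis) and total bilirubin up to 1.5 x ULN, with a separate provision for Gilbert's syndrome. Section 4.2 excludes chronic liver disease and earlier transaminitis of grade II or worse.

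**Working it through.** The plan gives no figure on this point, so the main check sets the texts side by side.

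**Step 1: overlap of thresholds.** Section 8.8 starts above 3 x ULN, so it overlaps all three ALT/AST rows. The table below assumes that the other 8.8 criteria are met.

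| Example | Meets 8.8? | Duvelisib under Table 7.6 | Nivolumab under Table 7.6 |
|---|---|---|---|
| ALT 4 x ULN, bilirubin 2.5 x ULN | Yes, SAE | Continued | Withheld to grade 1 |
| ALT 8 x ULN, bilirubin 2.5 x ULN | Yes, SAE | Held, then same dose once ALT/AST is below 3 x ULN (first occurrence) | Permanently stopped |
| ALT above 20 x ULN, bilirubin 2.5 x ULN | Yes, SAE | Discontinued | Permanently stopped |

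The gap for duvelisib is therefore in the first two bands.

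**Step 2: does any other text require a hold?**
- Section 11 covers infections, diarrhea/colitis, skin reactions, pneumonitis and neutropenia. It has no liver subsection and refers back to 7.6.
- Section 8.1 defines DLTs for escalation decisions and does not set an individual patient's dose.
- Sections 8.2.1, 8.2.2 and 8.8 cover classification and reporting.
- Section 4.4.1 allows stopping for an unacceptable adverse event, without a liver criterion.

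None makes potential DILI a trigger to hold duvelisib.

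**Step 3: does the table use such qualifiers elsewhere?** Yes. For platelets of 25K to below 50K, duvelisib is unchanged with grade 1 bleeding but withheld with grade 2 bleeding. For suspected PJP, duvelisib is held until evaluation. Total bilirubin is already in the liver panel (section 6.4.1), so the missing qualifier could be applied with data already collected.

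**Step 4: exposure in the 3-5 x ULN band.** The dose levels are from Table 7.5; the time in the band is assumed. Weekly dose = 7 x capsules per day x mg per capsule.
- 15 mg daily: 7 x 1 x 15 = 105 mg per week; 420 mg over an assumed 4 weeks.
- 25 mg daily: 7 x 1 x 25 = 175 mg per week; 700 mg over 4 weeks.
- 25 mg BID: 7 x 2 x 25 = 350 mg per week; 1400 mg over 4 weeks.

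Under a hold each figure is 0 mg.

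**Step 5: how often.** The documents give no rate. With up to 42 patients (section 14.0) and an assumed per-patient rate r, P(at least one) = 1 - (1 - r)^42 and the expected number is 42r.

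| Assumed r | P(at least one) | Expected number |
|---|---|---|
| 0.5% | 0.19 | 0.21 |
| 1% | 0.34 | 0.42 |
| 2% | 0.57 | 0.84 |
| 5% | 0.88 | 2.1 |

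**Step 6: side effect of a hold in phase I.** Sections 12.1 and 14.1.1 ask for 75% of pills to have been taken. Holding 7 of 28 days leaves 21/28 = 75%; holding 8 leaves 20/28 = 71%. A hold of 8 or more days in cycle 1 could therefore take a patient with liver toxicity out of the cohort analysis. Section 14.1.2 defines an evaluable patient differently, so this is a risk rather than a certainty.

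**The case against.** The strongest reply is that the table does not stand alone. Section 7.6 describes it as drawn from the two package inserts and as incomplete, and sends clinicians to the ASCO guideline for more detail. Its column is headed as recommended management. Section 11 ties management to clinical context. A potential-DILI SAE form must be sent within one business day, with the duvelisib manufacturer among the recipients (section 8.2.2). The DSMB reviews SAEs, discusses changes needed for patient safety and can suspend accrual (section 10.1). The 3-5 x ULN row is also not passive: it withholds nivolumab, requires at least weekly monitoring, and raises steroids if the abnormality persists with symptoms.

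All of this stands as far as it goes, and it lowers the severity. It shows that a hold is allowed and that the event would be seen. It does not show that a hold is required. A statement that a table is incomplete helps with situations the table leaves out; here the ALT/AST value falls in a row that gives an explicit instruction.

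A reader might go further and infer that the protocol obliges sites to continue duvelisib in potential DILI, or that the cited guideline and inserts also lack a rule for combined bilirubin elevation. The documents support neither. Investigators keep discretion, and the outside sources are not available here and may well cover the case. The exposure and probability figures are likewise not evidence of harm: they follow from assumed durations and rates.

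**Conclusion.** The point holds as a gap in the protocol's own dosing text. In two ALT/AST bands (>3 to 5 and >5 to 20 x ULN), meeting section 8.8 changes reporting but not duvelisib dosing. A site that follows the rows literally would continue the drug in the first band and could resume it at full dose in the second.

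The size is modest: probably few patients or none, but a potentially serious injury in any one of them. The conclusion rests on the protocol text alone, on reading the rows as written, and on no assumption about event rate. It is a safety clarification worth making because it is cheap. It does not show that patients will be harmed or that DILI is unmonitored.

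**What to change.** Add one row to Table 7.6 that overrides all ALT/AST rows, for ALT/AST above 3 x ULN when section 8.8 is met:

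- Withhold both duvelisib and nivolumab pending evaluation, and check ALT/AST and total bilirubin at least weekly.
- If no non-study cause is found, discontinue duvelisib unless the investigator documents nivolumab as the more likely cause. Section 14.2.3.4 already attributes toxicity to both drugs unless the investigator judges one the likelier culprit.
- If a non-study cause is found, return to the applicable ALT/AST row.
- Any stricter action in the >5 x and >20 x ULN rows, such as permanent nivolumab discontinuation, still applies.

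Limit the maintain-dose instruction in the 3-5 x ULN row to patients who do not meet 8.8. The new row has to span the bands. A change confined to 3-5 x ULN could stop duvelisib at ALT 4 x ULN yet leave full-dose rechallenge at 8 x ULN, giving the worse injury the laxer rule.

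Also state that a hold under this row does not remove a phase I patient from the DLT cohort analysis through the 75%-of-pills rule.

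Cost: one row, one qualifier and one sentence. Weekly bilirubin adds one test per 2 weeks while visits are 2-weekly and three per 4 weeks once they are 4-weekly, in affected patients only. Section 8.0 already requires a physician's causality assessment. The drawback is an occasional interruption in a patient whose injury proves to have another cause; at 15 mg daily, a second interruption for the same toxicity means discontinuation under the Table 7.7 note. Sample size, the DLT definition and the efficacy endpoints do not change.
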